8.2.3. Serious Adverse Events

A serious adverse event is any untoward medical occurrence at any dose that:

- Results in death;
- Is life-threatening (immediate risk of death);
- Requires inpatient hospitalization or prolongation of existing hospitalization;
- Results in persistent or significant disability/incapacity (substantial disruption of the ability to conduct normal life functions);
- Results in congenital anomaly/birth defect.

Or that is considered to be:

• An important medical event.

Medical and scientific judgment is exercised in determining whether an event is an important medical event. An important medical event may not be immediately life-threatening and/or result in death or hospitalization. However, if it is determined that the event may jeopardize the subject or may require intervention to prevent one of the other AE outcomes, the important medical event should be reported as serious.
Examples of such events are intensive treatment in an emergency room or at home for allergic bronchospasm; blood dyscrasias or convulsions that do not result in hospitalization; or development of drug dependency or drug abuse.

8.2.4. Hospitalization

Hospitalization is defined as any initial admission (even less than 24 hours) in a hospital or equivalent healthcare facility, or any prolongation of an existing admission. Admission also includes transfer within the hospital to an acute/intensive care unit (eg, from the psychiatric wing to a medical floor, medical floor to a coronary care unit, or neurological floor to a tuberculosis unit). An emergency room visit does not necessarily constitute a hospitalization; however, the event leading to the emergency room visit is assessed for medical importance.

Hospitalization does not include the following:

- Rehabilitation facilities;
- Hospice facilities;
- Respite care (eg, caregiver relief);
- Skilled nursing facilities;
- Nursing homes;
- Same-day surgeries (as outpatient/same-day/ambulatory procedures).

Hospitalization or prolongation of hospitalization in the absence of a precipitating clinical AE is not in itself an SAE. Examples include:

- Admission for treatment of a preexisting condition not associated with the development of a new AE or with a worsening of the preexisting condition (eg, for workup of a persistent pretreatment laboratory abnormality);
- Social admission (eg, subject has no place to sleep);
- Administrative admission (eg, for yearly physical examination);
- Protocol-specified admission during a study (eg, for a procedure required by the study protocol);
- Optional admission not associated with a precipitating clinical AE (eg, for elective cosmetic surgery);
- Hospitalization for observation without a medical AE;

• Preplanned treatments or surgical procedures. These should be noted in the baseline documentation for the entire protocol and/or for the individual subject.

Diagnostic and therapeutic noninvasive and invasive procedures, such as surgery, should not be reported as SAEs. However, the medical condition for which the procedure was performed should be reported if it meets the definition of an SAE. For example, an acute appendicitis that begins during the reporting period should be reported if the SAE requirements are met, and the resulting appendectomy should be recorded as treatment of the AE.

8.3. Severity Assessment

If required on the AE page of the CRF, the investigator will use the adjectives MILD, MODERATE, or SEVERE to describe the maximum intensity of the AE. For purposes of consistency, these intensity grades are defined as follows:

Severity Assessment		
MILD	Does not interfere with subject's usual function.	
MODERATE	Interferes to some extent with subject's usual function.	
SEVERE	Interferes significantly with subject's usual function.	

Note the distinction between the severity and the seriousness of an AE. A severe event is not necessarily an SAE. For example, a headache may be severe (interferes significantly with the subject's usual function) but would not be classified as serious unless it met one of the criteria for SAEs, listed above.

8.4. Special Situations

8.4.1. Protocol-Specified Serious Adverse Events

There are no protocol-specified SAEs in this study. All SAEs will be reported to Pfizer Safety by the investigator as described in previous sections, and will be handled as SAEs in the safety database.

8.4.2. Potential Cases of Drug-Induced Liver Injury

Humans exposed to a drug who show no sign of liver injury (as determined by elevations in transaminases) are termed "tolerators," while those who show transient liver injury, but adapt are termed "adaptors." In some subjects, transaminase elevations are a harbinger of a more serious potential outcome. These subjects fail to adapt and therefore are "susceptible" to progressive and serious liver injury, commonly referred to as drug-induced liver injury (DILI). Subjects who experience a transaminase elevation above 3 times the upper limit of normal (× ULN) should be monitored more frequently to determine if they are an "adaptor" or are "susceptible."

In the majority of DILI cases, elevations in aspartate aminotransferase (AST) and/or alanine aminotransferase (ALT) precede total bilirubin (TBili) elevations (>2 × ULN) by several days or weeks. The increase in TBili typically occurs while AST/ALT is/are still elevated above $3 \times ULN$ (ie, AST/ALT and TBili values will be elevated within the same lab sample). In rare instances, by the time TBili elevations are detected, AST/ALT values might have decreased. This occurrence is still regarded as a potential DILI. Therefore, abnormal elevations in either AST OR ALT in addition to TBili that meet the criteria outlined below are considered potential DILI (assessed per Hy's law criteria) cases and should always be considered important medical events, even before all other possible causes of liver injury have been excluded.

The threshold of laboratory abnormalities for a potential DILI case depends on the subject's individual baseline values and underlying conditions. Subjects who present with the following laboratory abnormalities should be evaluated further as potential DILI (Hy's law) cases to definitively determine the etiology of the abnormal laboratory values:

- Subjects with AST/ALT and TBili baseline values within the normal range who subsequently present with AST OR ALT values >3 × ULN AND a TBili value >2 × ULN with no evidence of hemolysis and an alkaline phosphatase value <2 × ULN or not available;
- For subjects with baseline AST **OR** ALT **OR** TBili values above the ULN, the following threshold values are used in the definition mentioned above, as needed, depending on which values are above the ULN at baseline:
 - Preexisting AST or ALT baseline values above the normal range: AST or ALT values >2 times the baseline values AND >3 × ULN; or >8 × ULN (whichever is smaller);
 - Preexisting values of TBili above the normal range: TBili level increased from baseline value by an amount of at least 1 × ULN or if the value reaches >3 × ULN (whichever is smaller).

Rises in AST/ALT and TBili separated by more than a few weeks should be assessed individually based on clinical judgment; any case where uncertainty remains as to whether it represents a potential Hy's law case should be reviewed with the sponsor.

The subject should return to the investigator site and be evaluated as soon as possible, preferably within 48 hours from awareness of the abnormal results. This evaluation should include laboratory tests, detailed history, and physical assessment.

In addition to repeating measurements of AST and ALT and TBili, laboratory tests should include albumin, creatine kinase (CK), direct and indirect bilirubin, gamma-glutamyl transferase (GGT), prothrombin time (PT)/international normalized ratio (INR), total bile acids, alkaline phosphatase and acetaminophen drug and/or protein adduct levels. Consideration should also be given to drawing a separate tube of clotted blood and an

anticoagulated tube of blood for further testing, as needed, for further contemporaneous analyses at the time of the recognized initial abnormalities to determine etiology. A detailed history, including relevant information, such as review of ethanol, acetaminophen (either by itself or as a coformulated product in prescription or over-the-counter medications), recreational drug, supplement (herbal) use and consumption, family history, sexual history, travel history, history of contact with a jaundiced person, surgery, blood transfusion, history of liver or allergic disease, and potential occupational exposure to chemicals, should be collected. Further testing for acute hepatitis A, B, C, D, and E infection and liver imaging (eg, biliary tract) may be warranted.

All cases demonstrated on repeat testing as meeting the laboratory criteria of AST/ALT and TBili elevation defined above should be considered potential DILI (Hy's law) cases if no other reason for the liver function test (LFT) abnormalities has yet been found. Such potential DILI (Hy's law) cases are to be reported as SAEs, irrespective of availability of all the results of the investigations performed to determine etiology of the LFT abnormalities.

A potential DILI (Hy's law) case becomes a confirmed case only after all results of reasonable investigations have been received and have excluded an alternative etiology.

8.4.3. Exposure to the Investigational Product During Pregnancy or Breastfeeding, and Occupational Exposure

Exposure to the investigational product under study during pregnancy or breastfeeding and occupational exposure are reportable to Pfizer Safety within 24 hours of investigator awareness.

8.4.3.1. Exposure During Pregnancy

For both unapproved/unlicensed products and for marketed products, an exposure during pregnancy (EDP) occurs if:

- A female becomes, or is found to be, pregnant either while receiving or having been exposed (eg, because of treatment or environmental exposure) to the investigational product; or the female becomes or is found to be pregnant after discontinuing and/or being exposed to the investigational product;
 - An example of environmental exposure would be a case involving direct contact with a Pfizer product in a pregnant woman (eg, a nurse reports that she is pregnant and has been exposed to chemotherapeutic products).
- A male has been exposed (eg, because of treatment or environmental exposure) to the investigational product prior to or around the time of conception and/or is exposed during his partner's pregnancy.

If a subject or subject's partner becomes or is found to be pregnant during the subject's treatment with the investigational product, the investigator must report this information to Pfizer Safety on the CT SAE Report Form and an EDP supplemental form, regardless of

whether an SAE has occurred. In addition, the investigator must submit information regarding environmental exposure to a Pfizer product in a pregnant woman (eg, a subject reports that she is pregnant and has been exposed to a cytotoxic product by inhalation or spillage) to Pfizer Safety using the EDP supplemental form. This must be done irrespective of whether an AE has occurred and within 24 hours of awareness of the exposure. The information submitted should include the anticipated date of delivery (see below for information related to termination of pregnancy).

Follow-up is conducted to obtain general information on the pregnancy and its outcome for all EDP reports with an unknown outcome. The investigator will follow the pregnancy until completion (or until pregnancy termination) and notify Pfizer Safety of the outcome as a follow-up to the initial EDP supplemental form. In the case of a live birth, the structural integrity of the neonate can be assessed at the time of birth. In the event of a termination, the reason(s) for terminated fetus should be specified and, if clinically possible, the structural integrity of the terminated fetus should be assessed by gross visual inspection (unless pre-procedure test findings are conclusive for a congenital anomaly and the findings are reported).

If the outcome of the pregnancy meets the criteria for an SAE (ie, ectopic pregnancy, spontaneous abortion, intrauterine fetal demise, neonatal death, or congenital anomaly [in a live-born baby, a terminated fetus, an intrauterine fetal demise, or a neonatal death]), the investigator should follow the procedures for reporting SAEs.

Additional information about pregnancy outcomes that are reported to Pfizer Safety as SAEs follows:

- Spontaneous abortion includes miscarriage and missed abortion;
- Neonatal deaths that occur within 1 month of birth should be reported, without regard to causality, as SAEs. In addition, infant deaths after 1 month should be reported as SAEs when the investigator assesses the infant death as related or possibly related to exposure to the investigational product.

Additional information regarding the EDP may be requested by the sponsor. Further follow-up of birth outcomes will be handled on a case-by-case basis (eg, follow-up on preterm infants to identify developmental delays). In the case of paternal exposure, the investigator will provide the subject with the Pregnant Partner Release of Information Form to deliver to his partner. The investigator must document in the source documents that the subject was given the Pregnant Partner Release of Information Form to provide to his partner.

8.4.3.2. Exposure During Breastfeeding

Scenarios of exposure during breastfeeding must be reported, irrespective of the presence of an associated SAE, to Pfizer Safety within 24 hours of the investigator's awareness, using the CT SAE Report Form. An exposure during breastfeeding report is not created when a Pfizer drug specifically approved for use in breastfeeding women (eg, vitamins) is administered in

accord with authorized use. However, if the infant experiences an SAE associated with such a drug's administration, the SAE is reported together with the exposure during breastfeeding.

8.4.3.3. Occupational Exposure

An occupational exposure occurs when, during the performance of job duties, a person (whether a healthcare professional or otherwise) gets in unplanned direct contact with the product, which may or may not lead to the occurrence of an AE.

An occupational exposure is reported to Pfizer Safety within 24 hours of the investigator's awareness, using the CT SAE Report Form, regardless of whether there is an associated SAE. Since the information does not pertain to a subject enrolled in the study, the information is not recorded on a CRF; however, a copy of the completed CT SAE Report Form is maintained in the investigator site file.

8.4.4. Medication Errors

Other exposures to the investigational product under study may occur in clinical trial settings, such as medication errors.

Safety Event	Recorded on the CRF	Reported on the CT SAE Report Form to Pfizer Safety Within 24 Hours of Awareness
Medication errors	All (regardless of whether	Only if associated with an
	associated with an AE)	SAE

Medication errors may result from the administration or consumption of the investigational product by the wrong subject, or at the wrong time, or at the wrong dosage strength.

Medication errors include:

- Medication errors involving subject exposure to the investigational product;
- Potential medication errors or uses outside of what is foreseen in the protocol that do or do not involve the participating subject.

Such medication errors occurring to a study participant are to be captured on the medication error page of the CRF, which is a specific version of the AE page.

In the event of a medication dosing error, the sponsor should be notified immediately.

Whether or not the medication error is accompanied by an AE, as determined by the investigator, the medication error is recorded on the medication error page of the CRF and, if applicable, any associated AE(s), serious and non-serious, are recorded on an AE page of the CRF.

Medication errors should be reported to Pfizer Safety within 24 hours on a CT SAE Report Form **only when associated with an SAE**.

9. DATA ANALYSIS/STATISTICAL METHODS

Detailed methodology for summary and statistical analyses of the data collected in this study is outlined here and further detailed in a SAP, which will be maintained by the sponsor. The SAP may modify what is outlined in the protocol where appropriate; however, any major modifications of the primary endpoint definitions or their analyses will also be reflected in a protocol amendment.

9.1. Sample Size Determination

Approximately 98 subjects will be randomized in a ratio of 1:2:2:2 to four treatment groups A:B:C:D, where A is the placebo group. Assuming an approximate 14% dropout rate this will ensure a minimum of 84 subjects complete the study. This sample size (12 for the placebo group and 24 for the each of monotherapy groups and the combination group) is estimated to provide >90% power to detect a difference of 30% mean reduction in whole liver fat from MRI-PDFF relative to placebo for the PF-05221304 + PF-06865571 combination using a 1-sided Type I error rate of 0.05. This randomization schema will enable detection of a smaller effect requires a larger sample size and hence the sample size is increased for the active arms. With the sample size of 24 completers for each of the PF-05221304 + PF-06865571 combination relative to each monotherapy is approximately 90% using a 1-sided Type I error rate of 0.25. These calculations assume a pooled standard deviation of the log-relative change of 0.32 (based on an internal study).

9.2. Analysis of the Primary Endpoint

The analysis population for primary endpoint analyses will include all randomized subjects who received at least 1 dose of IP (Full Analysis set).

The primary endpoint will be the relative change from baseline to Day 42 in whole liver PDFF. Baseline will be the closest measurement prior to first dose on Day 1. An analysis of covariance (ANCOVA) will be performed on log-transformed relative change from baseline with treatment and baseline diabetes as factors, and log-transformed baseline whole liver PDFF value as a covariate. Estimates of the mean relative changes between placebo and each active drug arm (PF-05221304 monotherapy, PF-06865571 monotherapy and PF-05221304 plus PF-06865571 combination) at Day 42, and the corresponding 90% confidence interval (CI) will be obtained from the model. Similarly, PF-05221304 plus PF-06865571 combination will be compared to each monotherapy through estimates of the mean relative change and corresponding 50% and 90% confidence intervals. No adjustment for multiple comparisons will be made. If the model does not fit the data group medians and their differences from the placebo median will be presented. The details will be provided in the SAP.

Descriptive summaries of the observed values and percent change from baseline in whole liver PDFF for each treatment group will also be produced.

9.3. Analysis of Secondary Endpoints

Secondary endpoints relate to safety and tolerability whose analyses are described in Section 9.7.

9.4. Analysis of Tertiary/Exploratory Endpoints

Percent changes from baseline in LFTs will be summarized; group medians and pairwise differences from the comparators will be presented. Log-transformed relative changes from baseline in lipid panel parameters will be analyzed separately using mixed model for repeated measures (MMRM) with treatment, study day and interaction of treatment with study day as factors, log-transformed baseline values of the dependent variable, baseline diabetes status and log-transformed baseline whole liver PDFF as covariates.

If the model does not fit the data model reduction techniques might be employed; otherwise, group medians and their differences from the placebo median will be presented. Details will be provided in the SAP.

For all other pharmacodynamic endpoints/biomarkers to be included in the CSR observed values, changes from baseline and/or percent changes from baseline will be summarized descriptively at all collection time points. Details and any additional analyses will be described in the SAP.

CCI	

9.6. Analysis of Other Endpoints

Pharmacogenomic and biomarker data will be collected and retained for future analyses, but will not be analyzed for the purposes of CSR.

9.7. Safety Analysis

AEs, ECGs, BP, pulse rate, and safety laboratory data will be reviewed and summarized on an ongoing basis during the study to evaluate the safety of subjects. Any clinical laboratory, ECG, BP, and pulse rate abnormalities of potential clinical concern will be described. Safety data will be presented in tabular and/or graphical format and summarized descriptively, where appropriate.

Physical examination information collected during the course of the study will be considered source data and will not be required to be reported, unless otherwise noted. However, any

untoward findings identified on physical examinations conducted during the active collection period will be captured as AEs, if those findings meet the definition of an AE.

Data collected at screening that are used for inclusion/exclusion criteria, such as laboratory data, ECGs, and vital signs, will be considered source data, and will not be required to be reported, unless otherwise noted. Demographic data collected at screening will be reported.

Vital Signs Analysis

Changes from baseline in systolic blood pressure, diastolic blood pressure and pulse rate will be summarized by treatment and time. The number (%) of subjects with maximum increases from baseline will be tabulated by treatment as defined in the SAP. Numbers and percentages of subjects meeting the categorical criteria will be provided and individual values listed in the study report. No formal inferential statistics will be applied to the vital signs data.

Electrocardiogram Analysis

Changes from baseline for the ECG parameters QT interval, heart rate, QTcF interval, PR interval, and QRS interval will be summarized by treatment and time. QTcF will be derived using Fridericia's heart rate correction formula. The number (%) of subjects with maximum increases from baseline will be tabulated by treatment as defined in the SAP. Numbers and percentages of subjects meeting the categorical criteria will be provided and individual values listed in the study report. No formal inferential statistics will be applied to the ECG data.

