## Mixed Model for Repeated Measurements (MMRM)

This model will be used for the analysis of endpoints with more than one post-Baseline collection time point. All observed data collected during the post-Baseline treatment period will be utilized. The MMRM analysis will be performed with treatment, study day and treatment-by-study day interaction as fixed effects, Baseline value of the analysis endpoint, and Baseline whole liver PDFF. If the endpoint being analyzed is log-tranformed, the Baseline value of the analysis endpoint and the Baseline whole liver PDFF will also be log-transformed. Repeated measures model with unstructured correlation matrix will be utilized. If this does not converge then compound symmetry structure will be considered. Additionally, the number of covariates may be reduced to improve model fit. Estimates of

treatment effects will be assessed using least square means (LSMs) and CIs at each time point. LSM difference for each comparison along with the CIs and 2-sided p-values will be provided. If there are major deviations from the statistical assumptions underlying this model then alternative transformations (eg, log) or non-parametric analyses may be presented. Justification for any alternative to the planned analysis will be given in the study report.

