# Vital Signs

Absolute values and changes from Baseline in seated systolic and diastolic blood pressure and pulse rate will be summarized by treatment and study day, according to sponsor reporting standards. Tables will be paged by parameter. Baseline is as defined in Section 3.5.3.

Mean changes from Baseline for systolic and diastolic blood pressure and pulse rate will be plotted against study day. On each plot there will be one line for each treatment, with all treatments on the same plot, including the placebo.

For Baseline subtracted seated systolic and diastolic blood pressure and pulse rate, the differences between each dose and placebo (dose – placebo) will be summarized (N, mean, 90% CI) and plotted (mean, 90% CI) for each dose and day including follow-up.

Maximum absolute values and maximum changes from Baseline for vital signs, over all measurements taken post-dose after randomization will also be tabulated by treatment using categories as defined in the Appendix. Numbers and percentages of subjects meeting the categorical criteria will be provided. All planned and unplanned post-dose time points will be counted in these categorical summaries. All values meeting the criteria of potential clinical concern will be listed.

Maximum decrease and increase from Baseline for seated systolic and diastolic blood pressures, and maximum increase from Baseline for seated pulse rate will be summarized by treatment, according to sponsor reporting standards.

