## Electrocardiogram

Absolute values and changes from Baseline in QT, heart rate, QTcF, QTc, PR, and QRS will be summarized by treatment and day using sponsor reporting standards. Tables will be paged by parameter. Baseline is as defined in Section 3.5.4.

Mean changes from Baseline in QT, heart rate and QTcF will be plotted against study day. On each plot there will be one line for each treatment, with all treatments on the same plot including the placebo.

In addition for Baseline subtracted QT, heart rate and QTcF, the differences between each dose and placebo (dose – placebo) will be summarized (N, mean, 90% CI) and plotted (mean, 90% CI) for each dose and day including follow-up.

ECG endpoints and changes from Baseline (QTcF, PR and QRS) will also be summarized descriptively by treatment using categories as defined in the Appendix (for QTc these correspond to ICH E14). Numbers and percentages of subjects meeting the categorical criteria will be provided. All planned and unplanned postdose timepoints will be counted in these categorical summaries. All values meeting the criteria of potential clinical concern will be listed.

Maximum absolute value (post-dose after randomization) and the maximum increase from Baseline for QTcF, PR and QRS will be summarized by treatment according to sponsor reporting standards.

Listings of subjects with any single post-dose value >500 msec will also be produced for QTcF.

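### SAP 6.6 gives differences from placebo with 90% intervals for six blood pressure, pulse and ECG parameters as unadjusted change scores; adjusting for the Day 1 value would be a minor, nearly free gain in precision

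*Protocol*

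**What the plan says.** Protocol 9.7 describes vital signs and ECG by arm and time ("Changes from baseline in systolic blood pressure, diastolic blood pressure and pulse rate will be summarized by treatment and time") and then limits their status: "No formal inferential statistics will be applied to the vital signs data" and, for the ECG, "No formal inferential statistics will be applied to the ECG data". It mentions no difference from placebo and no interval.

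The between-arm intervals appear only in SAP 6.6. Under Vital Signs: "For Baseline subtracted seated systolic and diastolic blood pressure and pulse rate, the differences between each dose and placebo". Under Electrocardiogram: "In addition for Baseline subtracted QT, heart rate and QTcF, the differences between each dose and placebo". Both are to be tabulated as N, mean and 90% CI and plotted, for each day including follow-up. Six parameters are covered. PR and QRS are not. Neither paragraph names a model, a least-squares mean or a covariate.

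SAP 5.2 has a repeated-measures model with "treatment, study day and treatment-by-study day interaction as fixed effects, Baseline value of the analysis endpoint", plus baseline whole liver PDFF. It is introduced in general terms: "This model will be used for the analysis of endpoints with more than one post-Baseline collection time point". SAP Table 3 applies it to liver enzymes and lipids. Section 6.6 does not mention it, although the Schedule of Activities places vital signs and ECG at Visits 7 to 11.

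**The concern.** Vital signs and ECG belong to the secondary endpoint (Protocol 2, SAP 3.2). Each baseline is one seated reading or one ECG on Day 1 (Protocol 7.2.3 and 7.2.4), so it carries measurement noise. Subtracting a noisy baseline over-corrects: an arm that starts high by chance tends to appear to fall, and an arm that starts low tends to appear to rise. The comparison arm is small, with about 14 randomized to placebo and 12 expected to complete. The exploratory liver enzymes and lipids get a baseline covariate, while these safety comparisons do not.

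At stake is the precision of the plotted differences from placebo and how they read when the arms happen to differ on Day 1. There is also a specification gap. The general sentence in SAP 5.2 could be taken to cover these endpoints and SAP 6.6 reads as if it does not, so two programmers could produce different intervals from the same SAP.

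**Working it through.** **Inputs.** Arm sizes are in Protocol 9.1: "This sample size (12 for the placebo group and 24 for the each of monotherapy groups and the combination group"). Protocol 3.1 gives 14 and 28 randomized. No SD and no baseline-to-visit correlation r is given for blood pressure, pulse or ECG, so r is an assumption, shown from 0.3 to 0.95. The SD s is taken as equal at both times.

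**The plan's own figures.** With 14% dropout, 84/0.86 = 97.7, so 98; 12/0.86 = 13.95, so 14; 24/0.86 = 27.9, so 28. For liver fat, the standard error is 0.32 × √(1/12 + 1/24) = 0.113. Then |ln 0.70|/0.113 = 3.15, and 3.15 − 1.645 = 1.51, giving power of 0.934. This agrees with the stated figure of more than 90%. The documents give no width or power for the vital sign or ECG intervals.

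**Precision.** Per-subject variances are:
- raw change: 2(1−r)s²
- baseline-adjusted: (1−r²)s²

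The large-sample width ratio is therefore √((1+r)/2). With 12 against 24, the adjusted interval has 33 rather than 34 degrees of freedom and pays for estimating a slope. This multiplies the ratio by about (1.692/1.691) × √(1 + 1/32) = 1.016.

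| r | √((1+r)/2) | × 1.016 | Narrower by |
|---|---|---|---|
| 0.3 | 0.806 | 0.819 | 18% |
| 0.5 | 0.866 | 0.880 | 12% |
| 0.7 | 0.922 | 0.937 | 6% |
| 0.9 | 0.975 | 0.990 | 1% |
| 0.95 | 0.987 | 1.003 | none |

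Simulation (20,000 trials per r) gave the same ratios. With 14 against 28 they are almost identical (0.82, 0.88, 0.94, 0.99, 1.00). When all 84 completers are pooled in both analyses they are 0.81, 0.87, 0.93, 0.98 and 0.99.

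**Illustration, assuming s = 10 mmHg for systolic pressure.** At r = 0.5 the raw 90% half-width is 1.691 × 10 × √(2 × 0.5) × 0.354 = 5.98 mmHg. The adjusted one is 1.692 × 10 × √0.75 × 0.354 × √(1 + 1/32) = 5.26 mmHg. At r = 0.7 the pair is 4.63 and 4.34; at r = 0.9 it is 2.67 and 2.65.

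**Chance imbalance.** If the arms differ by d at baseline, the expected later difference without a treatment effect is r·d, so the change-score difference is off by r·d − d = −(1−r)d. One standard error of d is s√(1/12 + 1/24) = 0.354s. The resulting shift is 0.25s at r = 0.3, 0.18s at 0.5, 0.11s at 0.7 and 0.04s at 0.9. With s = 10 mmHg and r = 0.5 that is about 1.8 mmHg, against a half-width of 5.98.

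**Validity.** In the same simulations, coverage of the raw 90% interval was 0.897 to 0.902 and the estimate averaged zero.

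**The case against.** The strongest reply is that these are descriptive displays on which nothing depends. The pausing criteria in Protocol 3.3 count adverse events and individual discontinuations. Repeat ECGs follow individual QTcF thresholds (Protocol 7.2.4). The predictive-probability criteria in SAP 7 use triglycerides and liver fat. Maximum changes, categorical tables and listings are unaffected by how an interval is computed. The planned intervals are also valid, r is unknown, and at high r the gain vanishes. Finally, the SAP 5.2 model includes baseline PDFF, so it cannot simply be invoked without saying what happens to that term.

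All of this stands, and it limits the point to a minor one. It does not remove the gain at low or moderate r. Nor does it explain why intervals between arms are published under a protocol that rules out formal inference, without a statement of how they are computed or what they are for.

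A reader might infer that the intervals under-cover. In simulation, the tenth of trials with the largest baseline imbalance in one direction did show raw coverage of about 80% at r = 0.5 and 84% to 85% at r = 0.7. That figure is conditional on an extreme draw; over all randomizations coverage is 90%. A reader might also infer that a safety decision could be misled, but no decision rule in the documents uses these intervals.

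**Conclusion.** A minor free improvement, not an error. On the natural reading of SAP 6.6, the six differences from placebo are raw change-score differences: unbiased and correctly covering, but less precise than they could be and shifted by −(1−r) times whatever baseline imbalance occurs. The gain runs from about 18% narrower at r = 0.3 to nothing near 0.95. It rests on assumed values of r, equal SDs at both times, and the completer counts; early visits will have nearer 14 on placebo, because the safety set is all treated subjects (SAP 4.3).

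The point does not extend to PR and QRS, for which no between-arm intervals are planned, or to the by-arm summaries in Protocol 9.7, which are sound as they stand. Protocol 9.7 matters only because its exclusion of formal inference sits unexplained beside the SAP's intervals.

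**What to change.** - In SAP 6.6, for systolic pressure, diastolic pressure, pulse rate, QT, heart rate and QTcF only, take the differences from placebo and their 90% CIs as least-squares mean differences from a model of the SAP 5.2 repeated-measures form on change from baseline. Its terms are treatment, study day, treatment by study day, and the subject's Day 1 value of the same parameter.
- State that baseline PDFF is omitted because it is not needed for these parameters. Say that the follow-up visit enters as a study day, since the SAP 6.6 display includes it and SAP 5.2 speaks of the treatment period.
- Keep the descriptive tables, categorical tables and listings unchanged.
- State in SAP 6.6, and align Protocol 9.7 to say, that these intervals are for estimation only and no hypothesis is tested. Accordingly, do not report the p-values that SAP 5.2 attaches to the model.

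The cost is a paragraph in the SAP, a sentence in the protocol and six model fits on data already collected. No visits, samples or subjects are added.
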